Animal assisted interactions with an animal robot during physical and occupational therapy sessions in the Pediatric ICU: A feasibility study (PCRG)

NCT05075395

25 Jan 2022

Study Protocol

Purpose

The purpose of this study is to evaluate the feasibility, acceptability, safety, and preliminary therapeutic treatment effects of PARO™, a therapeutic animal robot, during physical therapy and occupational therapy sessions with critically ill patients in the Pediatric ICU (PICU).

Background & Rationale

Symptom Experience in the PICU: Admission to the PICU can be an extremely upsetting experience for children of all ages. In addition to physical symptoms such as pain, thirst and fatigue, patients in the PICU also experience a multitude of psychological symptoms. Symptoms like anxiety, spells of terror, social isolation, disturbed sleeping patterns, restlessness, fear, confusion and loss of control are exacerbated in the PICU because patients often have limited mobility, decreased capacity to communicate, and rely on healthcare providers for survival.

Symptom Management in the PICU: Large doses of sedative and analgesic medications are administered by nursing staff to help alleviate distressing symptoms. Overuse of sedative medications can cause a sequelae of adverse effects and, therefore, recent recommendations call for reducing sedative use as much as possible. To minimize the overwhelming symptom burden of acute critical illness and promote lasting psychological well-being during recovery, it is imperative to identify effective non-pharmacological interventions that decrease psychological distress, but do not alter level of alertness during acute critical illness. Established evidence supports the use of a variety of non-pharmacological approaches that can be easily applied as adjuncts to sedative and analgesic medications in order to reduce dependence on these medications. Animal assisted interactions (AAI) are a promising integrative approach that can be used as an adjunct to sedative and analgesic medications in order to improve psychological symptoms and promote comfort, relaxation, and positive mood in critically ill patients.

AAI to Alleviate Symptoms in the ICU: AAI are interventions that intentionally incorporate animals as part of a therapeutic process to promote human health, learning, and well-being. Domestic and farm animals such as dogs, cats, birds, equines, guinea pigs, rabbits, llamas, sheep, goats, and pigs are predominantly featured in AAI programs. Animals can be simply observed, touched, held, and petted, or more actively integrated into specific therapy activities such as brushing with different tools to exercise range of motion and fine motor coordination and tandem walking with the animal to encourage exercise. Recent literature indicates that AAI can improve reality orientation and attention span, eliminate the sense of isolation, reduce stress and anxiety, enhance communication, promote positive social interactions, and enhance overall quality of life. The use of AAI in the ICU has the potential to engage patients, family members, and healthcare staff in an innovative, holistic approach to symptom management.

Benefits of Robotic Animals for AAI in the ICU: While additional research is warranted to further explore the potential impact of AAI on a variety of clinically meaningful patient outcomes, the highly technical, fast-paced ICU environment and the severely immunocompromised health statuses of ICU patients greatly limits the exploration of AAI in the ICU. A new frontier in animal robotics opens a vast array of opportunities to implement AAI in the critically ill population. Robot animals may be just as effective as live animals and may provide even more flexibility and tailoring in order to meet the needs of diverse

situation that arise in the ICU. In addition, the infection control risk that live animals pose to critically ill patients may be significantly lessened.

Methods

At the patient's first physical/occupational (PT/OT) appointment, the PT/OT provider will assess whether eligibility criteria are met. If so, the study will be presented to the patient and their parent or guardian. If the patient is interested in participating, the PI or PI's research assistant (RA) will obtain written informed consent. Pretest data collection is next, followed by the therapy session with PARO. The PI or RA will remain in the room during therapy session to record field notes. After completion of the therapy session, the PI or RA will begin post-test data collection. The participant will remain in the study for up to 7 PT/OT sessions or until discharge from the PICU.

The Patient Demographic Form will be administered to all participants prior to the initial PT/OT session with PARO. Data specific to the PARO intervention (Psychological and Physiological Variables, Activity Performance), will be collected via a face-to-face interview within 30 minutes prior to and within 30 minutes after each PT/OT session with PARO. ATP testing will occur prior to each new subject enrollment to ensure participant safety. Semi-structured interviews will be conducted with the participant and an intervention satisfaction measure will be administered after the protocol is complete (either after 7 PT/OT sessions with PARO or at ICU discharge).

Only one participant will be enrolled at a time. Participants & therapists will be required to practice hand hygiene before and after use of PARO. During the protocol, PARO will be kept in a hard plastic pet carrier which is brought to the participant's room for the PT/OT sessions. A sheet or towel will be placed under PARO anytime it is placed on a bed, table, chair, etc. to avoid direct contact with surfaces in the room. Once the PT/OT session is done, the PARO is returned to the PI's office in the carrier. The PARO is removed from the carrier, which is cleaned with a PDI Super Sani-Cloth wipe. The PARO is then cleaned per the Daily Cleaning Protocol. This entails moving a Rapid Razor-UV™ cordless handheld sanitizer over the entire PARO surface, pausing over each area for 20 to 30 seconds. The PARO is returned to the carrier after cleaning.

Prior to a new enrollment or if the PARO is visibly soiled, it will be deep cleaned per the Deep Cleaning Protocol. This involves spraying the PARO's fur with Dapple cleaner and wiping with a towel, avoiding the area around eyes and nose. Next the fur is wiped with a PDI Super Sani-Cloth and left to dry. Lastly, the fur is brushed with a brush sprayed with Clorox bleach and allowed to dry again. Cleanliness is tested by swabbing 14 locations on the PARO which are checked with the ATP monitoring system with SystemSURE Plus Process. All test results must be below the established RLU threshold of 30. If any of the areas tested do not meet the threshold, the entire PARO will be cleaned again. Once all areas tested fall below the 30 RLU threshold, the PARO is placed in its carrier.

Statistical Analysis Plan

Sample Size

Prior studies of PARO™ in other non-ICU settings have shown moderate to large effect sizes. A sample in the range of 20-25 is adequate for single-group efficacy studies when population effect sizes are likely to be moderate or larger. Since we are unsure of the exact expected effect size in the ICU, we have increased our sample size to 30.

Analysis

All data collected will be entered directly into REDCap and exported into SPSS 24 for data analysis. For Aim 1, establishing the feasibility and acceptability of PARO™ for critically ill patients admitted to the PICU, feasibility will be calculated by comparing total consent and refusal rates, attrition rates, and the number of full therapy sessions completed. Refusal and attrition rates will be evaluated using point estimates and confidence intervals. Intervention acceptability will be assessed by summarizing scores from the Patient Satisfaction Measure. Descriptive statistics will be used to summarize individual scores, including mean, standard deviation, range, median, and interquartile range. A content analysis on the results from the semi-structured interviews will be conducted.

For Aim 2, exploring safety considerations related to infection control [participant hospital-acquired infection (HAI) rates, screening for the presence of microbial contamination with real-time ATP testing], any hospital acquired infection obtained while in the PICU will be tracked. The ATP scores after each deep cleaning session will be plotted for graphical trends.

For Aim 3, examining the therapeutic effect of PARO on patient psychological variables (pain, anxiety) physiological variables (heart rate, blood pressure, respiratory rate, oxygen saturation), and sedative and analgesic medication requirements will be recorded pre- and post-test. These scores will be summarized using descriptive statistics and the distributions of psychological and physical variables will be assessed for normality. Therapeutic effects for normally distributed variables will be assessed with paired samples t-tests to assess changes as a result of PARO. Wilcoxon signed rank tests will be used for variables found to be non-normal.

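### A child who withdraws before seven sessions or ICU discharge has no planned satisfaction score or interview, so the acceptability summary may be somewhat optimistic (minor)

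*Combined protocol and SAP*

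**What the plan says.** **Timing of the acceptability data (Methods).** The satisfaction measure is "administered after the protocol is complete (either after 7 PT/OT sessions with PARO or at ICU discharge"). The semi-structured interview is tied to the same moment. Planned participation ends at the same two points: "The participant will remain in the study for up to 7 PT/OT sessions or until discharge from the PICU".

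**Data from individual sessions (Methods).** Two kinds of information exist for any session a child attends. One is observation: "The PI or RA will remain in the room during therapy session to record field notes". The other is the set of measures taken before and after each session: "Data specific to the PARO intervention (Psychological and Physiological Variables, Activity Performance), will be collected via a face-to-face interview". Satisfaction is not among them.

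**Aim 1 (Statistical Analysis Plan, Analysis).** For feasibility, "feasibility will be calculated by comparing total consent and refusal rates, attrition rates, and the number of full therapy sessions completed". Refusal and attrition receive point estimates and confidence intervals. For acceptability the plan has two components: "Intervention acceptability will be assessed by summarizing scores from the Patient Satisfaction Measure", described by mean, SD, range, median and interquartile range; and "A content analysis on the results from the semi-structured interviews will be conducted". The text does not say how many children the satisfaction summary will cover, and gives no rule for absent scores.

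**Aim 3 (same section).** The measures taken before and after sessions serve the treatment-effect analysis: "Therapeutic effects for normally distributed variables will be assessed with paired samples t-tests to assess changes as a result of PARO". No analysis of the field notes is stated.

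**The concern.** Acceptability is one of the study's stated purposes and half of Aim 1. The plan allows for children leaving, because it makes attrition an Aim 1 outcome. Yet a child who withdraws from the study before either data-collection point gives neither a score nor an interview, and these are the only two sources the SAP uses for acceptability.

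A child who leaves because PARO is disliked or frightening is the most informative case for acceptability. If such children are missing, mean satisfaction will look better than it was among all children who met PARO, and the interviews will lack their reasons. The attrition rate shows how many left, not why. Nor can analysis recover an interview that was never held, so any remedy has to be made at data collection.

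No go/no-go threshold is attached to satisfaction. What is at stake is the reading of this study and the planning of a later one, not a formal decision.

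**Working it through.** **Step 1. Who is affected.** Set the two collection points against the ways a child can stop:

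| Course | Score and interview planned? |
|---|---|
| Completes seven sessions | Yes |
| Discharged from the ICU before seven sessions | Yes, at discharge |
| Stops PARO but stays in the study until discharge | Yes on a natural reading, at discharge, though not spelled out |
| Withdraws from the study before either point | No |

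Only the last row is a gap.

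**Step 2. Whether other planned data fill it.** Field notes and session measures, including pain and anxiety, exist for the sessions a withdrawing child attended. The SAP assigns the session measures to Aim 3 and states no use for the notes. They may hint at a reason for leaving, but they are neither a satisfaction score nor an interview.

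**Step 3. Size of the possible bias in the mean.** The plan has no figure of its own to reproduce: it gives no expected attrition, no score scale and no reasons for leaving. The inputs are:

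- N = 30, the sample size in the SAP, Sample Size; it is an assumption that all 30 have at least one PARO session.
- w = number of unscored withdrawers (assumed 0, 1, 3 or 6).
- d = (mean of those scored − mean the withdrawers would have given) / SD of those scored (assumed 0.5 or 1).

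The formulas, in SD units, are:

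- Overstatement = (w/30) × d
- Standard error of the scored mean = 1/√(30 − w)
- Ratio = overstatement / standard error

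| w | w/30 | SE | Overstatement, d = 0.5 | Ratio | Overstatement, d = 1 | Ratio |
|---|---|---|---|---|---|---|
| 0 | 0 | 0.183 | 0 | 0 | 0 | 0 |
| 1 | 0.033 | 0.186 | 0.017 | 0.09 | 0.033 | 0.18 |
| 3 | 0.10 | 0.192 | 0.05 | 0.26 | 0.10 | 0.52 |
| 6 | 0.20 | 0.204 | 0.10 | 0.49 | 0.20 | 0.98 |

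For the last row with d = 1: 0.20 × √24 = 0.98.

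With d = 0 the bias is zero for every w. With d = −1 the mean is understated by 0.033, 0.10 or 0.20 SD for w = 1, 3 or 6. A ratio above 1 needs heavier assumptions: for example, w = 9 and d = 1 give 0.30 × √21 = 1.37.

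This covers the mean only. It does not apply to the median and interquartile range, which the SAP also plans, or to the loss of interview content.

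**The case against.** The strongest case against acting has four parts.

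**The group is narrow and the effect small.** Early discharge is covered, and the bias stays below one standard error in every tabulated case, all of which rest on assumed inputs. The sign could reverse. This stands, and it is why the point is minor.

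**Attrition already gives a warning.** It is reported under the same aim as satisfaction, with a confidence interval, so heavy loss would be visible. This stands in part: the reader would see how many left, but not whether PARO was the cause. The number of scores might well be reported anyway; stating it in advance costs nothing.

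**The record is incomplete.** A reader might infer that reasons for leaving are recorded nowhere. The documents do not support that. Consent pages were removed and the data-entry forms are not reproduced, so either could deal with withdrawal. What can be said is that the visible Methods and SAP text describe no such record. The timing rule for the satisfaction measure is explicit and is unaffected by this limit.

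**A remedy may recover little.** Families who withdraw fully may be the least willing to complete a form. This is fair, though even a few replies, or a clear count of those missing, would help. It may also be tempting to substitute field notes in the content analysis for families who decline. That would set staff observation for withdrawers against participants' own words for everyone else, so the evidence would differ by withdrawal status. It is better not done.

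**Conclusion.** The point holds at minor severity. Followed as written, the plan measures acceptability only in children who reach seven sessions or ICU discharge, while separately counting attrition under the same aim.

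The summary is optimistic only if some children withdraw before either point and those children are, on average, less satisfied. The documents establish neither condition. A reader might infer that satisfaction will be overstated, or that every child with fewer than seven sessions goes unscored. The first is a possibility of unknown size and direction. The second is contradicted by the discharge provision.

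Under the assumptions shown (30 treated children, withdrawers 0.5 to 1 SD less satisfied), one to three unscored withdrawers would shift the mean by 0.02 to 0.10 SD, at most about half its standard error. Six with a 1 SD gap would shift it by about one standard error. With few withdrawals, the likelier loss is the withdrawers' reasons rather than any material distortion of the mean.

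**What to change.** **Methods.** Add withdrawal from the study as a third point at which the existing Patient Satisfaction Measure and a short interview are offered, where the family agrees. Include the reason for stopping in that interview.

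**Statistical Analysis Plan, Analysis, Aim 1.** Report the number of children scored out of all children with at least one PARO session. List any reasons given for leaving beside the attrition rate. Do not add field notes to the content analysis only for families who decline.

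**Cost.** A small wording change in two places, using the same form and staff; because only one participant is enrolled at a time, the extra work is slight. Some withdrawing families will decline, so the gap may shrink without closing, and reported acceptability may be slightly lower.

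### Aim 3 attributes the single-group pre/post change to PARO, but no session without PARO is described, so the paired tests cannot separate PARO from the therapy session

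*Combined protocol and SAP*

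**What the plan says.** The Analysis section of the SAP introduces Aim 3 as "examining the therapeutic effect of PARO on patient psychological variables", followed by physiological variables and medication use. Pre/post differences are to be tested with paired t-tests, or Wilcoxon signed rank tests for non-normal variables, "to assess changes as a result of PARO".

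The Methods place the psychological and physiological measurements "within 30 minutes prior to and within 30 minutes after each PT/OT session with PARO". On duration they say: "The participant will remain in the study for up to 7 PT/OT sessions or until discharge from the PICU". Sedative and analgesic use is not in the Methods list of data collected around each session. The SAP says only that "sedative and analgesic medication requirements will be recorded pre- and post-test", without a time window.

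The Sample Size section supports the choice of 30 by calling 20-25 "adequate for single-group efficacy studies when population effect sizes are likely to be moderate or larger". No control arm, PARO-free session, substitute object or crossover is described anywhere.

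**The concern.** The two Aim 3 phrases are causal: they name PARO as the source of the change. Each before/after window contains the whole therapy session as well as PARO, the passage of time, concurrent care and a researcher in the room taking notes. Heart rate, blood pressure, respiratory rate, oxygen saturation and pain could all plausibly move with physical therapy alone. A report that follows the plan's wording could therefore credit PARO with a change it did not cause. It could equally miss a PARO benefit that an opposite session effect cancels. Either result could then be carried into the planning of a later trial as if it were a PARO effect.

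**Working it through.** **1. The plan's own figure.** The sample size of 30 comes with no alpha, sidedness, power, numeric effect size or SD, so it cannot be strictly reproduced. If two-sided 5% and 80% power are assumed, a paired t-test needs 34 children at a standardised change of 0.5, 24 at 0.6 and 21 at 0.65. The stated 20-25 thus corresponds to about 0.66 down to 0.58, and 30 to about 0.53. All of these concern detecting a change of any origin. None concerns a change specific to PARO.

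**2. What the data contain.**
- Children: 30 (Sample Size).
- Sessions per child: up to 7, fewer if PICU discharge comes first (Methods).
- Maximum pre/post pairs: 30 × 7 = 210.
- Pairs described without PARO: 0. The first PT/OT appointment is used for eligibility and consent, and then leads into pretest and the session with PARO, so it supplies no PARO-free measurement.

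**3. What the paired test estimates.** For any outcome measured around the session, write

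mean change = (PT/OT session) + (PARO) + (time, concurrent care, observation).

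The trial observes only the left-hand side. PARO is present in every pair, so the terms on the right always occur together and no analysis of these data can separate them. Adding children narrows the confidence interval around the sum and leaves its composition unknown.

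**4. Illustration of the consequence.** Assumed: two-sided 5%, one pair per child, n = 30, no attrition. The documents give no session-only shift, so the shifts below are also assumed.

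Smallest significant observed mean change:

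t(0.975, 29) / √30 = 2.045 / 5.477 = 0.373 SD of the change score.

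If PARO adds nothing and everything else shifts the outcome by δ SD of the change score, the rejection probability is that of a noncentral t with 29 degrees of freedom and noncentrality δ√30:

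| δ (assumed) | δ√30 | P(significant) |
|---|---|---|
| 0 | 0 | 0.050 |
| 0.2 | 1.095 | 0.185 |
| 0.5 | 2.739 | 0.754 |

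Simulation with 200,000 runs per row gives 0.050, 0.186 and 0.755. This is the ordinary power curve of a paired t-test. It shows that the test responds to a shift from any source. It is not an estimate of this trial's error rate.

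**The case against.** The strongest reply is that the documents already limit the claim. The title calls this a feasibility study, and the Purpose section lists "feasibility, acceptability, safety, and preliminary therapeutic treatment effects of" PARO. The Methods consistently describe the exposure as a therapy session with PARO, the single-group design is openly stated, and the limits of an uncontrolled comparison are commonly discussed in the report. No analysis, estimate or safety step would change, so this could be called a matter of wording.

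Part of that stands. The design suits Aims 1 and 2, nothing is concealed, and no decision rule uses Aim 3. But calling the effects preliminary signals that they are uncertain. It does not say that they are inseparable from the therapy session, and no section says so. The Sample Size section's reference to efficacy studies points the other way. The SAP prespecifies how a significant result will be read, and the reading it prespecifies is one the design cannot support.

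Two narrower objections concern the remedy. The SAP does not say how up to seven sessions per child enter one paired test, so session-level wording might not fit every possible analysis. The Methods, however, define pretest and post-test as bracketing the session, which supports that wording. It is also unclear whether medication use is formally tested or only summarised. Either way it falls under the claim of a therapeutic effect, and the fix gives it neutral wording. Finally, the figures in the illustration rest on assumptions, and the conclusion does not depend on them.

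**Conclusion.** The concern holds. As written, Aim 3 claims an effect of PARO that a single-group design with no PARO-free session cannot identify. From the documents alone: at most 210 pairs, none without PARO, so the session-only change cannot be estimated and the size and sign of any misattribution are unknown. The illustrative 0.37 SD threshold and the 19% and 75% rejection probabilities depend on the assumed alpha, shifts, one pair per child and no attrition. The point should be fixed but is limited in reach. It concerns the causal wording and a missing statement of limitation. The single-group design, the tests and the feasibility and safety aims are not in question.

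**What to change.** In the Aim 3 paragraph of the SAP:

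1. Replace both causal phrases (the therapeutic effect of PARO, and changes resulting from PARO) with *change over a PT/OT session that included PARO*.
2. Add: *Without PT/OT sessions that omit PARO, this change cannot be attributed to PARO separately from the therapy session, time or concurrent care.*
3. For sedative and analgesic requirements, which have no stated window, write *change from pre-test to post-test*, with the same sentence.

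Reporting each change with a 95% confidence interval would be a useful addition, but it does not solve attribution.

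The cost is a weaker Aim 3 claim. Design, data collection, sample size, tests and Aims 1 and 2 stay as they are. A PARO-free comparator would be needed to isolate PARO, but that is not asked of this feasibility study. For scale, with assumed two-sided 5%, 80% power and a PARO increment of 0.5 SD of the change score, parallel groups would need 2 × (1.960 + 0.842)² / 0.5² ≈ 63 children per arm. Splitting the planned 30 into 15 per arm would give about 28% power.
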